# 11.2 Serious Adverse Events (SAEs)

- 11.2.1 A SAE is any AE that results in any of the following outcomes:
  - Death
  - Immediate threat to life
  - Hospitalization or prolongation of an existing hospitalization
  - Persistent or significant disability/incapacity
  - Congenital anomaly/birth defect
- 11.2.2 Important medical events that do not result in one of these outcomes, but based on appropriate medical judgment, are deemed to jeopardize the subject or require medical or surgical intervention to avert one of the listed outcomes, may also be considered SAEs at the Investigator's discretion.
  - Allergic reactions are a known risk with clear aligners. Subjects with known plastic allergies have been excluded from this study.

**CONFIDENTIAL:** The information in this study protocol is strictly confidential and is available for review to Investigators, study center personnel, the ethics committee, and the health authorities. It will not be disclosed to third parties without written authorization from the Sponsor, except to obtain informed consent from persons receiving the study treatment. Once the protocol is signed, its terms are binding for all parties.

As there may be some subjects enrolled who are unaware of a plastic allergy, allergic reactions will not be documented as SAEs. They should however be documented as Adverse Events (AE).

- 11.2.3 Any AE considered serious (SAE) according to the criteria above that occurs during the study must also be documented by the Investigator and recorded in the **eCRF**.All deaths and immediately life-threatening events, whether related or unrelated, will be recorded on the SAE Form and documented via the eCRF system within 24 hours of Investigators awareness.
- 11.2.4 All SAEs will be followed until satisfactory resolution has been reached, or until the Investigator deems the SAE to be chronic or the subject to be stable.
- 11.2.5 All SAEs must also be reported by the Sponsor as soon as possible to the IRB.
- 11.2.6 It is the responsibility of the device Sponsor to report the event as specified in 21 CFR Part 812.46. All SAEs designated as "unrelated" to the product will be reported to the FDA at least annually in a summary format by the Sponsor.
- 11.2.7 Subjects will be notified of any unexpected SAEs within the timelines specified by the U.S. CFR.

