  - Possibly Related: A direct cause and effect relationship between the investigational device and the AE has not been demonstrated, but there is a reasonable possibility that the AE was caused by the investigational device.
  - Probably Related: The AE is likely related to the investigational device. This category applies when the experience most likely seems to be related to the investigational device but there is a modest suspicion that it could be related to other causes.
  - Related: There is a direct cause and effect relationship between the AE and the investigational device.
- 11.1.7 The medical assessment of related AE severity will be determined by

using the following definitions:

- Mild: The AE is easily tolerated and does not interfere with usual activity.
- Moderate: The AE interferes with daily activity, but the subject is still able to function.
- Severe: The AE is incapacitating, and the subject is unable to work or complete usual activity, i.e. a serious injury has occurred.
- Life Threatening: The SAE places the subject, in the view of the Investigator, at immediate risk of death from the reaction as it occurred, i.e., it does not include a reaction that had it occurred in a more severe form, might have caused death.
- 11.1.8 Outcome may be classified as resolved, ongoing, resolved with sequelae, or death.
  - Unexpected severe or life threatening related events will be followed until resolved (the subject's health has returned to his/her baseline status or all variables have returned to normal), an outcome is reached, stabilization (the Investigator does not expect any further improvement or worsening of the AE), or the event is otherwise explained regardless of whether the subject is still participating in the study.
  - Where appropriate, medical testing and examinations will be performed to document AE resolution.
- 11.1.9 The types of adverse events that are known to occur with orthodontic treatment include mild to moderate gum pain, inflammation, and redness; allergic reaction to plastic(s) or metal(s); and root resorption.

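### Section 11.2.2 exempts allergic reactions from SAE documentation with no limit by outcome; read literally, this conflicts with 11.2.1 and, for deaths and immediately life-threatening events, with 11.2.3

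*Combined protocol and SAP*

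**What the plan says.** All of the following is in the combined protocol and SAP.

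- **Definition, 11.2.1.** "A SAE is any AE that results in any of the following outcomes", followed by a list: death, immediate threat to life, hospitalization, lasting disability, birth defect. No type of event is excepted.
- **Discretionary category, 11.2.2.** This opens with "Important medical events that do not result in one of these outcomes" and lets the investigator still call such events SAEs on medical judgment.
- **Exemption, in a sub-bullet of 11.2.2.** After noting that allergic reactions are a known aligner risk and that known plastic allergy is excluded, it says: "As there may be some subjects enrolled who are unaware of a plastic allergy, allergic reactions will not be documented as SAEs". The next sentence has them recorded as AEs.
- **Recording, 11.2.3.** "All deaths and immediately life-threatening events, whether related or unrelated, will be recorded on the SAE Form", with eCRF documentation within 24 hours of the investigator's awareness. Allergy is not excepted.
- **Duties tied to the SAE label.** 11.2.4: "All SAEs will be followed until satisfactory resolution has been reached", or until the event is judged chronic or the subject stable. 11.2.5: "All SAEs must also be reported by the Sponsor as soon as possible to the IRB".
- **Endpoint, 9.1.** The primary safety endpoint is the incidence of related AEs and SAEs, compared between the arms.

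**The concern.** Whether an event is serious should follow from what happened to the subject. Here one sentence removes a whole class of events from the SAE category by diagnosis. The reason it gives is that some enrolled subjects may not know of their allergy. That reason concerns who gets into the study, not how severe the reaction is, so it applies as much to a hospitalized subject as to one with a mild rash.

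Two things are at stake. First, a serious reaction to a risk that the protocol itself names could miss SAE follow-up, IRB reporting and the SAE count. IRB reporting matters more here because 12.3.1 plans no data safety monitoring board. Second, with up to 15 sites (synopsis), sites that read the sentence broadly and sites that read it narrowly would label the same event differently.

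**Working it through.** The plan states no figure on this point, so the check is a comparison of clauses, with one line of arithmetic for scale.

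**Step 1. Apply each clause to an allergic reaction, by outcome.**

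| Outcome of the allergic reaction | 11.2.1 | 11.2.2, literal | 11.2.3 | Result |
|---|---|---|---|---|
| Death | SAE | not an SAE | SAE Form | 11.2.2 against 11.2.1 and 11.2.3 |
| Immediate threat to life | SAE | not an SAE | SAE Form | 11.2.2 against 11.2.1 and 11.2.3 |
| Hospitalization | SAE | not an SAE | no separate rule for this outcome | 11.2.2 against 11.2.1 |
| Lasting disability | SAE | not an SAE | no separate rule for this outcome | 11.2.2 against 11.2.1 |
| No listed outcome, but important medically | not covered | not an SAE; discretion removed | no separate rule | no conflict with 11.2.1 |

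In the first two rows 11.2.3 gives sites a specific instruction that still catches the event. In the next two, 11.2.3 only refers back to the SAE criteria, and those are what is in dispute. The practical gap is therefore mainly hospitalization and lasting disability.

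**Step 2. Apply the narrow reading.** If the exemption reaches only events under the lead-in of 11.2.2, the first four rows are SAEs and the conflict disappears. The last row remains: the investigator could not upgrade an allergic reaction that needed intervention to prevent a listed outcome, although any other type of event could be upgraded. No other section says which reading applies.

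**Step 3. List what an event loses with the label, and what it keeps.**

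- Lost: the follow-up rule of 11.2.4, IRB reporting under 11.2.5, and a place among the SAEs in 9.1.
- Kept: recording as an AE with severity, treatment and outcome (11.1.2, 11.1.3), reporting to the complaint officer and regulatory compliance (11.1.1), review at visits (8.3.4), and follow-up of safety events after discontinuation (8.10.3). If related, it also stays among the related AEs in 9.1.
- Uncertain: 11.1.8 has its own follow-up rule for related events that are severe or life-threatening, but only if unexpected. Since 11.1.9 lists allergic reaction among the known events, a site could take that rule not to apply.

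**Step 4. Scale.** Section 4.2 plans 50 subjects per arm. One relabelled event changes that arm's SAE incidence by 1/50 = 0.020, or 2.0 percentage points. An expected number of such events cannot be calculated: 7.1.2 calls plastic allergy rare, inclusion criterion 10 removes known cases, and no frequency is given.

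**The case against.** The strongest defence is placement. The sentence continues a sub-bullet of 11.2.2, whose lead-in covers only events without a listed outcome. Read in place, it withholds investigator discretion for lesser allergic reactions and leaves 11.2.1 and 11.2.3 untouched. This is a fair reading and possibly the intended one. It does not settle the matter, because the sentence itself is unqualified and the reason it gives is not tied to outcome. What stands is that the conflict belongs to the literal reading and that the scope is ambiguous.

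The second defence is limited consequence. The events are rare and remain on record as AEs, fatal and life-threatening cases are caught by 11.2.3, and neither 9.1 nor 12.3 sets an SAE threshold or an SAE-specific test. All of this stands, and it limits the weight of the point.

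A reader might go further in three ways that the documents do not support:

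- **A third conflict, with 11.1.7.** That section words its life-threatening grade as "The SAE places the subject, in the view of the Investigator, at immediate risk of death from the reaction as it occurred". But it is a severity scale for related AEs, not a rule on what is documented as an SAE. It has no fatal grade, and the other grades speak of an AE. It adds nothing to the conflict with 11.2.1 and 11.2.3.
- **A biased comparison between arms.** Both arms use the same plastic (6.1.1), so the between-arm difference may move little.
- **A larger effect per event, from the minimum of 23 evaluable subjects per arm.** That number counts compliant completers. Safety is collected from device application (12.3.2), and data from withdrawn subjects are retained and used (16.4.3), so completers are not the natural denominator.

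**Conclusion.** The inconsistency is real on the literal text, and no other section resolves it. Followed as written, 11.2.2 takes SAE status from an allergic reaction that 11.2.1 makes an SAE. The cases that matter most are hospitalization and lasting disability, where nothing else in 11.2 restores the label.

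The size is modest and cannot be quantified as an effect on counts. The figure of 2.0 points per event assumes 50 subjects in the arm's safety denominator, which the plan does not define, and is for scale only. The loss is in SAE follow-up, IRB reporting and the absolute SAE count. It would be wrong to infer that serious allergic reactions disappear from the safety data or that deaths would go unrecorded: the AE record and 11.2.3 prevent that. This is a point that should be fixed. It does not put the trial's main comparison in doubt.

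**What to change.** Reconcile 11.2.2 with 11.2.1 and 11.2.3. Preferably, replace the exemption sentence and the one after it with: *Allergic reactions are classified as AE or SAE by the same criteria as any other event.* This restores the protocol's own definition and also returns the discretion for medically important events.

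The minimum alternative is to keep the exemption but limit it expressly to allergic reactions that meet no outcome listed in 11.2.1. That removes the contradiction, but leaves allergic reactions as the one event type that an investigator may not upgrade under 11.2.2.

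Either way the cost is a change to two sentences and to any matching site instruction, and possibly a few more SAE reports. No study procedure or analysis method changes.

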# 11.3 Device Deficiencies (DDs)

- 11.3.1 Device Deficiency (DD) is defined as: Inadequacy of a medical device with respect to its identity, quality, durability, reliability, usability, safety, or performance.
  - Device deficiencies include malfunctions, use errors, and inadequacy in the information supplied by the manufacturer including labelling.
  - This definition includes device deficiencies related to the investigational medical device or the comparator.
- 11.3.2 All DDs must be reported to the divisional complaint officer and regulatory compliance.

# 12. DATA AND STATISTICAL ANALYSIS

[figure not shown]
#### 12.1 Statistical Sample Size and Power (provided as an example)

12.1.1 The current study is a controlled prospective study to determine the expressed movements demonstrated by investigational device, Nighttime Aligners for 10-12 continous hours per day/night compared to the control group, Daytime Aligners, which are worn for 20-22 hours per day.

**CONFIDENTIAL:** The information in this study protocol is strictly confidential and is available for review to Investigators, study center personnel, the ethics committee, and the health authorities. It will not be disclosed to third parties without written authorization from the Sponsor, except to obtain informed consent from persons receiving the study treatment. Once the protocol is signed, its terms are binding for all parties.

12.1.2 Sample size calculations for this study were determined using statistical software Minitab to ensure proper powering. The desired sample size per arm is 23 based on power calculations previously developed by Dentsply Sirona. The desired level of power is 90%. The desired confidence is 95% (p <0.05). Calculations are based on a standard deviation of 1, a power value of 0.9 and a detected difference of 1. The calculation also assumes a 2-sided, alpha = 0.05 level of significance.

#### 12.2 Data Analysis

- 12.2.1 The Sponsor and Investigators are not blinded to the study data during the conduct of the trial, and may at periodic intervals analyze the data to assess study progress.
- 12.2.2 If nothing else is stated, descriptive statistics will be given for each variable in the clinical study and p-values may be complemented by confidence intervals as appropriate. When using the terminology descriptive statistics, it is meant that the number of subjects (N), mean, median, standard deviation (Sd), minimum (Min) and maximum (Max) values will be presented for continuous data and frequencies and percentages for categorical data.

- 12.2.3 All tooth movement data analyses will be performed using 3Shape Ortho System (K152086).
- 12.2.4 Three .stl files from each subject would be used for the analysis:
  - A pre-treatment STL file (TS) would be generated by scanning subject's pre-treatment intraoral scan taken before the start of treatment.
  - A planned or programmed STL (TP) file would be obtained from Archform Orthodontic Software System (K213916) after planned or programmed tooth movements have been made based on the treatment plan finalized by the digital lab and study Investigators.
  - The actual post-treatment STL file (TF) would be generated by scanning subject's post-treatment intraoral scan at the end of treatment.
- 12.2.5 Each STL file would convert into a Digital Study Model within the 3Shape Ortho System software to standardize the analysis.
- 12.2.6 Each DSM would be segmented using the "auto segmentation tool" of the software to demarcate each tooth separately.
- 12.2.7 This would be followed by Peer Assessment Rating (PAR) index to measure orthodontic treatment need and outcome (Richmond, 1992). This would be done using the built-in weighted PAR analysis tool of 3Shape Ortho System software. The PAR index will be performed by an external evaluator.
- 12.2.8 The weightage for each component of the PAR index would be set as: maxillary and mandibular anterior segment alignment x 1; buccal occlusion x 1; overjet x 6; overbite x 2; centerline x 4; following the ABO guidelines. The weighted PAR scores for each DSM would be compared as follows:

The PAR Score values for  $T_S$ ,  $T_P$ , and  $T_F$  will be transferred to the eCRF and the following will be calculated:

- Planned percentage reduction in PAR Score (Planned Improvement of Malocclusion [PIM]) = PAR Score TS- PAR Score TP / PAR Score TS \* 100
- Actual percentage reduction in PAR Score (Actual Improvement of Malocclusion [AIM]) = PAR Score TS- PAR Score TF / PAR Score TS \* 100
- Percentage of Accuracy of Outcome = 100% [(|PIM AIM|/|AIM|) \*100%]

Statistical analysis comparing the two treatment groups using the Wilcoxon rank sum test will pe performed. A two-sided p-value below

5% will be regarded as statistically significant. The null hypothesis of the study is that there is no difference between the two groups.

- 12.2.9 Additional comparisons between treatment groups may be performed and p-values presented using the Wilcoxon rank sum test. Wilcoxon signed rank test may be used for analysis within treatment groups over time.
- 12.2.10 Calculation of Spearman's rank correlation coefficients will be performed to elucidate the relationships between the accuracy of outcome with treatment duration, number of aligners, subject pain levels, and overall subject and doctor satisfaction for each group.
- 12.2.11 All methods used in this clinical study have been previously published and reviewed (Griffith 2021, Grünheid 2022). All data in this clinical study will be analyzed by an independent contractor to remove bias. Any adjustments or modifications to these methods will be duly documented and reported.

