EFFECTIVENESS ASSESSMENTS	Efficacy of Nighttime Aligners (worn 10-12 hours per day or night) will be assessed by demonstrating no statistically significant difference between expressed tooth movement versus programmed tooth movement at the end of treatment when compared to the Daytime aligners (worn 20-22 hours day/night). Quantification and comparison of expressed and programmed tooth movements will be conducted using Peer Assessment Rating (PAR) index to measure orthodontic treatment need and outcome, using the built-in weighted PAR analysis tool of 3Shape Ortho System software.
SAFETY ASSESSMENTS	The primary safety endpoint of the study will be the incidence of (device or dental) related AEs associated with the planned investigational treatment, as well as the occurrence of SAEs. Additionally, safety will be assessed through a post-treatment questionnaire administered to the subject asking about subject perceived comfort during treatment. Results will be quantified using a visual analogue scale. Both numerical values and a Wong Baker face scale will be used.
INCLUSION CRITERIA	
 
For inclusion in this clinical study subjects must meet all of the following criteria: 
 
Subject willing to participate in the clinical study and able to understand the content of the clinical study.
 
 
 
Subject must have permanent dentition (i.e. all second molars).
 
Subject must be 12 years of age or older.
 
Subject must be able to provide and sign consent for themselves, without requiring consent to be given by a legally authorized representative. Parental consent is also required for all participants who are not of the legal age to provide consent themselves (based on participant state of residence).
 
The subject requires correction of teeth without planned extrusive movements on either or both arches.
 

	
 
The subject has no greater than 5 mm of crowding and/or spacing (based on estimation by Investigator).
 

	
 
The subject does not require planned correction of molar tooth positions, posterior bite or molar classic relationship corrections. Subjects with Class II or Class III malocclusions requiring posterior bite / class correction are not eligible.
 

	
 
Subjects without prior orthodontic treatment within the past 18 months.
 

	9. Subjects who are periodontally stable.
	10. Subjects without a known history of plastic allergies.

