# 1. STUDY OBJECTIVES

# 1.1 **Primary Objective:**

The primary efficacy objective of this study is the comparison between groups of the quantification of actual vs planned tooth movements. Changes in tooth position from pre-treatment baseline to end of treatment results will be measured for both Daytime Aligners (control) and Nighttime Aligners (test).

The safety objective of the study will be the incidence of (device or dental) related AEs associated with the planned investigational treatment, in comparison to the incidence of AEs associated with control treatment.

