# Tooth movement treatment planning constraints of Nighttime Aligners (investigational):

Movement Type	Translate [B/L] (mm)	Torque / Incline (°)	Tip (°)	Rotate (°)	Intrude (mm)	Extrude (mm)
Per aligner	0.25 mm	1 °	1 °	1.6 °	0.1 mm	N/A
Tooth	Totals per treatment plan					
Incisors	5	25	25	45	2.5	N/A
Laterals	5	25	25	45	2.5	N/A
Canines	3	25	25	35	2.5	N/A
Premolars	2	10	10	10	1	N/A
Molars*	N/A	N/A	N/A	N/A	N/A	N/A

\*Movements of molar teeth are not in the treatment plans for these aligners.

6.1.3 Daytime Aligners are indicated for the treatment of tooth malocclusion in subjects with permanent dentition (i.e., second molars). The aligner system positions teeth by way of continuous gentle force. These aligners are to be worn by the subject 20-22 hours per day and night; aligners may be removed for small periods of time while eating, drinking or brushing.

Subjects will wear each aligner tray for 1-2 weeks, or as instructed by their dentist. When worn while sleeping, the therapy complements the circadian rhythm of bone remodeling and metabolism for tooth movement. Smaller incremental tooth movements are programmed into each aligner tray/stage allowing for activation of biological cascade governing orthodontic tooth movement, with an added advantage of intermittent force resulting in reduced root resorption. Daytime aligners (control) are made with material that is 0.30-0.35 inch thick and the planned tooth movement rate is 20% more than that of the Nighttime Aligners (investigational).

Tooth	movement	treatment	planning	constraints	of	Daytime	Aligners
(contro	ol):						

Movement Type	Translate [B/L] (mm)	Torque / Incline (°)	Tip (°)	Rotate (°)	Intrude (mm)	Extrude* (mm)
Per aligner	0.3 mm	1 °	1 °	2 °	0.1 mm	N/A
Tooth	Totals per treatment plan					
Incisors	5	25	25	45	2.5	N/A
Laterals	5	25	25	45	2.5	N/A
Canines	3	25	25	35	2.5	N/A
Premolars	2	10	10	10	1	N/A
Molars*	N/A	N/A	N/A	N/A	N/A	N/A

\*Extrusive and molar movements are allowable with standard, Daytime Aligners, however, for the purposes of this study, they will not be allowed.

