# 9.3 **Primary Efficacy Endpoint**

The primary effectiveness endpoint is the comparison between the treatment groups of the quantification of actual vs planned tooth movements using weighted Peer Assessment Rating (PAR) index.

• Planned percentage reduction in PAR Score (Planned Improvement of Malocclusion [PIM])

In addition comparison between treatment groups will also be performed for:

- Actual percentage reduction in PAR Score (Actual Improvement of Malocclusion [AIM])
- Percentage of Accuracy of Outcome

Quantification and comparison of expressed and programmed tooth movements will be conducted using to measure orthodontic treatment need and outcome, the built-in weighted PAR analysis tool of 3Shape Ortho System software (K152086).

- 9.3.1 The weighted PAR scores for each Digital Study Model (DSM) would be compared as follows:
  - Planned percentage reduction in PAR Score (Planned Improvement of Malocclusion [PIM]) = PAR Score TS- PAR Score TP / PAR Score TS \* 100
  - Actual percentage reduction in PAR Score (Actual Improvement of Malocclusion [AIM]) = PAR Score TS- PAR Score TF / PAR Score TS \* 100
  - Percentage of Accuracy of Outcome = 100% [(|PIM -AIM|/|AIM|) \*100%]

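### The objective is planned versus achieved tooth movement, but the only movement outcome is a total weighted PAR score, which can match the plan when its components do not and reflects premolar movement only indirectly

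*Combined protocol and SAP*

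**What the plan says.** Section 1.1 sets the primary efficacy objective as the "comparison between groups of the quantification of actual vs planned tooth movements" and adds: "Changes in tooth position from pre-treatment baseline to end of treatment results will be measured". The synopsis (Effectiveness Assessments) makes the success criterion "no statistically significant difference between expressed tooth movement versus programmed tooth movement at the end of treatment", judged against the Daytime arm.

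The section 6.1 tables limit planned movement by tooth type and movement type, in millimetres and degrees. Premolars have planned allowances in both arms; molars have none.

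Section 9.3 turns the objective into an endpoint: "quantification of actual vs planned tooth movements using weighted Peer Assessment Rating (PAR) index". Under 12.2.6 the models are segmented "to demarcate each tooth separately", and the next step is PAR scoring. Section 12.2.8 weights the components as "maxillary and mandibular anterior segment alignment x 1; buccal occlusion x 1; overjet x 6; overbite x 2; centerline x 4". It then says the PAR values for TS, TP and TF "will be transferred to the eCRF and the following will be calculated", namely planned improvement (PIM), actual improvement (AIM) and Percentage of Accuracy. No comparison of TP with TF by tooth, movement type or PAR component is specified.

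**The concern.** The question concerns positions of teeth; the data kept for analysis are three totals per subject. PAR summarises occlusion, and two different arrangements of teeth can share a total. Agreement of totals is therefore weaker evidence than agreement of movements.

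This matters more than usual because the hoped-for result is the absence of a significant difference. An outcome that responds weakly to some planned movements makes that result easier to reach, whether or not the arms really agree. The report could then claim more about tooth movement than its data measured.

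**Working it through.** The documents give no PAR values, so there is no stated figure to reproduce. The check evaluates the plan's own formulas on hypothetical scores.

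**Inputs.** Weights from 12.2.8: anterior alignment 1, buccal occlusion 1, overjet 6, overbite 2, centerline 4. Formulas from 9.3 and 12.2.8, read as:
- PIM = 100 × (TS − TP)/TS
- AIM = 100 × (TS − TF)/TS
- Accuracy = 100 − 100 × |PIM − AIM|/|AIM|

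The brackets in PIM and AIM and the minus sign in Accuracy are assumed; they do not appear in the text available to me.

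**Step 1: what Accuracy depends on.** Substituting, TS cancels within the ratio and Accuracy = 100 − 100 × |TF − TP|/|TS − TF|. It uses only totals. PIM, listed first in 9.3, contains no final score at all.

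**Step 2: when totals conceal differences.** For weighted component scores, |TF − TP| = |sum of (final − planned)|, which is at most the sum of |final − planned|. The two are equal unless the component differences have mixed signs. Mixed signs require at least one component to finish better (lower) than planned, so that component must have a planned residual and TP must exceed 0.

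**Step 3: a case that meets the condition.**

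| Weighted component | TS | TP | TF | Absolute TF − TP |
|---|---|---|---|---|
| Anterior alignment | 16 | 4 | 0 | 4 |
| Centerline (1 step × 4) | 4 | 0 | 4 | 4 |
| Total | 20 | 4 | 4 | 8 summed; 0 on totals |

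PIM = 16/20 = 80%; AIM = 16/20 = 80%; Accuracy = 100 − 0 = 100%. The planned centerline correction did not occur. The summed component difference is 8 points, half of the planned reduction of 20 − 4 = 16.

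**Step 4: cases that do not meet it.**
- Plan with no residual (TP = 0), TS = 20, one centerline step missed: TF = 4, PIM = 100%, AIM = 80%, Accuracy = 100 − 100 × 20/80 = 75%. The miss shows.
- Uniform shortfall with TS = 20, TP = 4 (fractional component scores allowed, as an idealisation). At 75% expression, TF = 20 − 0.75 × 16 = 8, AIM = 60%, Accuracy = 100 − 100 × 20/60 = 66.7%. At 50%, TF = 20 − 0.50 × 16 = 12, AIM = 40%, Accuracy = 100 − 100 × 40/40 = 0%. Both show clearly.

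**Step 5: premolars.** This does not depend on cancellation. The 6.1 tables allow premolars, in both arms, up to 2 mm translation, 10° each of torque, tip and rotation, and 1 mm intrusion per treatment plan. The only alignment component in 12.2.8 is for the anterior segments. A premolar that falls short of plan has no alignment component of its own and can reach the total only through another component, such as buccal occlusion. The documents do not give the scoring rules, so the size of that indirect effect cannot be stated.

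**The case against.** The strongest reply is that PAR is the declared measure: 9.3 names it openly, 12.2.11 says the methods are published, and choosing a summary occlusal index is legitimate. That stands. The point is not that PAR is invalid, but that section 1.1 promises a measurement of tooth position which this index does not supply.

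A reader might infer that cancellation would hide a general shortfall of the Nighttime aligners. The documents do not support this. Under-expression leaves components short of plan in the same direction, so the differences add, and dividing by AIM enlarges the effect. Step 3 needs a plan that deliberately leaves alignment points which treatment then corrects. Section 5.1 excludes subjects needing molar or posterior-bite correction, so any planned residual may lie mainly in buccal occlusion. That residual offsets a shortfall only if buccal occlusion finishes better than planned.

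A reader might also infer that failed torque, tip or rotation leaves little trace in the total. With only component names and weights given, that cannot be established.

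It can be said that the scans remain available and 12.2.9 permits further comparisons. Those are optional and undefined, and no provision requires component values to be recorded, so this does not close the gap.

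Finally, a summed absolute difference counts better-than-planned results as error. True, but the plan's own |PIM − AIM| does the same; showing signed differences answers it.

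**Conclusion.** The mismatch between objective and outcome is real and should be corrected. PAR is the only tooth-movement outcome; the satisfaction, comfort, pain and adverse-event endpoints do not measure movement. Total PAR can report full accuracy when components differ from plan, by 8 points against 16 planned in the illustration, but only with TP above 0 and a component finishing better than planned. The frequency is unknown. The premolar insensitivity holds whatever the value of TP, though its size is also unknown.

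It would go too far to conclude that the trial cannot answer its primary question. It can compare PAR-measured improvement between arms, and a uniform shortfall would be seen. What it cannot support is a statement about agreement of tooth positions. The arithmetic rests on hypothetical scores and on the reading of the formulas given above.

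**What to change.** 1. In 12.2.8, transfer the weighted component scores for TS, TP and TF to the eCRF alongside the totals.
2. Prespecify, as a supportive endpoint beside total PAR, each subject's sum over components of |TF − TP|, compared between arms with the Wilcoxon rank sum test already planned. Tabulate signed component differences by arm so that under- and over-correction can be told apart.
3. Reword 1.1 and the synopsis so that the conclusion concerns PAR-measured occlusal improvement. The exception is if a per-tooth comparison of TP with TF from the segmented models is shown to be feasible and is prespecified.

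Item 2 removes cancellation between components but stays within PAR, so it does not cure the premolar gap; item 3 deals with that.

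**Cost.** Items 1 and 2 are cheap, since components must be scored to form each total. The price is one more endpoint to place in the testing order, and item 3 narrows the stated claim. The per-tooth route should not be assumed cheap. The planned model comes from different software than the one used for scoring, and the documents describe no superimposition, per-tooth export or measurement error. Registering on the molars would assume they stay still, whereas the plan says only that no molar movement is programmed.
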